1.10 CLINICAL TRIAL PHASE Phase III

10.110BJECTIVES

Main: to know the incidence of postoperative delirium in patients at risk, over 65 years of age, treated early with prophylactic quetiapine compared to those treated with placebo.

Side:

- 1. Evaluate the safety and tolerability of the medication applied
- 2. To compare the efficacy of medication versus placebo in relation to:
 - length of hospital stay
 - perceived quality of life
 - all-cause mortality at discharge and 28±2 days from initiation (1st dose) of quetiapine treatment.
- 3 In cases where delirium develops, know:
 - Time of appearance
 - the duration and severity of the same
 - Total dose of treatment with other antipsychotics.

1.12STUDY DESIGN

Prospective low-level non-commercial, balanced, randomized, double-blind clinical trial (phase III) clinical trial.

1.13STUDY DISEASE

Delirium developed during the period after surgery.

Delirium is an acute alteration of consciousness accompanied by inattention, disorganization of thought and alterations of perception that fluctuate in a short period of time (DSM IV). It is one of the most frequent complications of surgery and develops characteristically between 0-96 h after the intervention. It is associated with worse prognosis in the short and long term.

1.14STUDY VARIABLES

- A. The main variable is the proportion of patients diagnosed with delirium (number of delirium cases/total number of patients) in the first 4 postoperative days in both branches.
- B. Secondary variables:
 - 1. number of days from the start of treatment to the onset of delirium, if it appears,
 - 2. duration of delirium, in days,
 - 3. severity of delirium measured with validated scale (DRS-R-98)
 - 4. total dose (mg) haloperidol or another antipsychotic to control symptoms of delirium,
 - 5. Security variables:
 - degree of sedation: by RASS scale,
 - QTc prolongation: increase in mseg on the control ECG.
 - presence or absence of extrapyramidal symptoms (tremor, involuntary movements, stiffness)
 - 6. days of hospital stay since surgery,

- 7. perceived quality of life (through SF36 validated questionnaire) 28±2 days after initiation of treatment,
- 8. All-cause mortality at discharge and 28±2 days after initiation of treatment

1.15STUDY POPULATION AND TOTAL NUMBER OF PATIENTS

Patients older than or equal to 65 years of age who are going to undergo major non-cardiac surgery and who have a score equal to or greater than 5 on the Delphi scale:

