4 HYPOTHESES AND OBJECTIVES

Hypothesis: The prophylactic administration of an antipsychotic with fewer side effects, such as quetiapine, in patients identified with a validated scale decreases the incidence of delirium during the postoperative period compared to placebo administration.

The main objective of the study is to determine the incidence of postoperative delirium in patients at risk, over 65 years of age, treated early with prophylactic quetiapine compared to those treated with placebo.

The secondary objectives are:

- eassess the safety and tolerability of the medication applied.
- cCompare the efficacy of medication versus placebo in relation to:
 - the length of hospital stay.
 - perceived quality of life at 28±2 days from the start (1st dose) of quetiapine treatment.
 - all-cause mortality at discharge and 28±2 days from initiation (1st dose) of quetiapine therapy.
- In cases where delirium develops, know:
 - Time of appearance.
 - the duration and severity of the same.
 - total treatment with other antipsychotics.

5 CLINICAL TRIAL DESIGN.

5.1 . DESCRIPTION OF VARIABLES

The main variable is the proportion of patients diagnosed with delirium (number of delirium cases/total number of patients) in the first 4 postoperative days. We will use a validated scale based on the DSM-IV definition of delirium, CAM: *Confusion Assessment Method* scale (17,24-27).

The secondary variables are:

- 1. Number of days from the start of treatment to the onset of delirium, if it appears.
- 2. duration of delirium, in days.
- 3. severity of theirium measured with validated scale (DRS-R-98).
- 4. D Total osis (mg) haloperidol or another antipsychotic tocontrol the symptoms of delirium.
- 5. Security Costs:
 - Sedation degree: using RASS scale.
 - QTc prolongation: increase in mseg in the control ECG.
 - presence or absence of extrapyramidal symptoms (tremor, involuntary movements, rigidity).
- 6. Days ofhospital stay of the surgical intervention.
- 7. perceived quality of life (through validated questionnaire SF36 or SF 12) 28±2 days after initiation of treatment.
- 8. mortality from all causes at discharge and 28±2 days after initiation of treatment.

Additional variables that will also be collected:

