6 PATIENT SELECTION AND WITHDRAWAL

6.1 INCLUSION CRITERIA.

Patients older than or equal to 65 years of age who are going to undergo major non-cardiac surgery and who have a score equal to or greater than 5 on the Delphi scale:

- Age: 70-79 years: 1 point; >80 years: 2 points.
- Physical activity: need for assistance, not self-sufficient: 2 pointss
- Alcoholism: 1 point.
- Hearing deficit: 1 point.
- History of delirium: 2 points.
- Urgent surgery: 1 point.
- Non-laparoscopic surgery: 2 points.
- Admission to Critical Units: 3 points.
- C-Reactive Protein (CRP) value > 10 mg/dL: 1 point.

6.2 EXCLUSION CRITERIA.

- × the lergia the quetiapine.
- × lactose intolerance.
- × patients with a score of less than 5 on the Delphi scale.
- × Diagnosis of delirium on admission.
- Cardiological diseases: QTc >460 msec in men, >470 msec in women, AMI or recent cardiac decompensation, AV block 2-3° or history of torsades de pointes arrhythmias or ventricular arrhythmias, bradycardia (<45 bpm).
- × hipopotasemia <3 mEq/CLK.
- × history of drug use.
- × Patients on antipsychotic or antidopaminergic treatment (chlorpromazine, clozapine, olanzapine, risperidone, haloperidol, quetiapine, paliperidone, amisulpride).
- × Parkinson's disease.
- × Minimental < 24.
- × vascular dementia or Levi's bodies.
- × Disorder of movements hipokinéticos.
- × History of neuroleptic malignant syndrome.
- × Central anticholinergic syndrome.
- × epilepsy.
- × patients weighing less than 50 or more than 200 kg.

× Patients participating in or having participated in a study of an investigational drug or device within four weeks prior to administration of the first dose of study treatment.

6.3 NUMBER OF PATIENTS.

Taking into account the current published literature, the estimated incidence of delirium in this type of population is 20-25%(2). We consider that a reduction in the absolute risk of delirium of 12% is clinically relevant , being similar to the reduction of absolute risk with non-pharmacological measures (10). Therefore, a sample size of 350 patients is estimated, with 175 subjects per treatment branch (significance level 95%, power 80%, expected losses of 5%).

6.4 EXPECTED CRITERIA FOR WITHDRAWAL OF STUDY SUBJECTS.

- 1. Voluntary patient abandonment: patients have the right to withdraw from the study at any time and for any reason, being able to express it personally or through their representative.
- 2. By medical criteria (safety and efficacy):

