If the sponsor terminates or suspends a trial, the investigator must inform the institution where the trial is conducted and the investigator/institutionmust promptly inform the CEIm by providing written justification of the reasons for the termination or suspension.

If the Ethics Committee (CEIm) terminates or withdraws the favourable opinion of a trial, the investigator shall inform the institution and the investigator/institution shall promptly inform the sponsor and provide written justification for the cause oftermination or suspension.

7 PATIENT TREATMENT.

7.1 CLINICALTRIAL MATERIALS.

The active drugwill be supplied by the promoter (IBSAL).

The manufacture of the medication will be entrusted to an independent company (LABORATORIUM SANITATIS, S.L.) which will generate identical capsules for active drugs and placebo under rules of good manufacture of medication according to current legislation. Subsequently, they will be sent to the pharmacy service of the C.A.U.S.A. Theperson in charge of dispensing the medication will be the only one who knows if the treatment is the active drug or is the placebo. All the medication that the patient will receive together will be dispensed, in a bottle containing the 6 corresponding capsules. The treating physician will leave reflected in the treatment orders: administrar quetiapine/placebo 1 capsule orally every 12 hours. The first dose of active drug/placebo will be administered 60 minutes after arrival at the resuscitation unit and every 12 hours thereafter for the first 3 postoperative days.

7.2 SCHEDULE OF VISITS AND PROCEDURES.

See Figure 1: Outline procedures in each visit.

- I. Pre-selection visit: where the patient is selected by assessing the inclusion and exclusion criteria. Itwill explain what the clinical trial consists of and give youthe documentation (information sheet and informed consent).
- II. Selection visit: it will be carried out during the pre-anesthesia consultation or the day before the surgical intervention. Thefollowing procedures shall be carried out:
 - signature of CI.
 - Verification of compliance with selection criteria.

- Demographics.
- Relevant medical history: Preoperative comorbidity.
- ASA classification.
- Preoperative medication: sleep medication, antidepressants, opiates, corticosteroids...
- vital signs.
- complete analysis with PCR.
- previous physical function: independent for activities of daily living (Barthel index).

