- Basal cognitive function (valued with MINIMental o 6 ICT).
- CAM scale.
- ECG and QTc measurement.
- III. Postoperative visits: A daily personal clinical visit will be made to all randomized patients during the first four days of the postoperative period or during the duration of their admission if it is less than 4 days. In this case, the last visit during admission will be the visit to discharge.

These clinical visits will be listed in corresponding to the postoperative day: visit 1st day post, visit 2nd day post... so on until the 4th postoperative day.

Procedures to be performed:

- CAM scale.
- RASS scale.
- Extrapyramidal symptoms.
- vital signs.
- ECG and QTc measurement (after administration of the 4th dose).
- Complete laboratory tests (at least one during the first four days after surgery).
- VAS scale and analgesia received (opiates).

In addition, during the 1st postoperative visit, the intraoperative variables will be collected:

- Type of surgical intervention and specialty.
- urgent ly programmed.
- anesthetic technique performed.
- Drugs used, doses and routes of administration(benzodiazepines, opiates, glucocorticoids, atropine).
- Measurement of anesthetic depth and/or regional brain oxygen saturation where possible.
- Duration anesthesia .
- EVA upon admission to URPA/Resuscitation.
- Analgesia: IV or by regional techniques(drug used, dose and administration).
- blood transfusion.

If the patient develops delirium, the daily visit will continue until the clinic disappears. In this case, the following will also be collected:

- severity of the picture using DRS scale -R- 98
- Drug used for its treatment, dose and route of administration.

- IV. Discharge visit: when the patient meets criteria and is discharged. The following will be collected:
 - Reason for hospital discharge.
 - CAM.
 - RASS.
 - vital signs.
 - Extrapyramidal symptoms.
 - Hospital evolution including complications that have appeared and that have required medical treatment (≥ grade II Clavien-Dindo scale): blood transfusion, surgical reoperation, pneumonia
 - mortality.
 - complete anal itatic if it has not been collected in the postoperative visits.
 - If you have developed delirium:
 - × duration.
 - × Severity.
 - × Dosage and route of administration of the drug used for its treatment.

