 - V. Premature withdrawal visit: all patients who, regardless of the cause and phase of the study in which they are, prematurely and permanently stop treatment, must complete the premature withdrawal visit, which will take place in the following 24-48 hours from the time the withdrawal is known. During the same the following procedures will be carried out:
 - reason de premature interruption.
 - vital signs.
 - CAM.
 - RASS.
 - sextrapyramidal symptoms.
 - Hospital evolution including complications that have appeared and that have required medical treatment (≥ grade II Clavien-Dindo scale): blood transfusion, surgical reoperation, pneumonia
 - if you have developed delirium:
 - × duration.
 - × severity.
 - × Dosage and route of administration of the drug used for its treatment.
- VI. Final visit: It will be carried out at 28± 2 days from the start of treatment. A personal, telephone or mail follow-up will be carried out to determine the vital status (mortality) and quality of life in relation to health through the SF 36 questionnaire. Complications that have appeared during this period and that have required medical treatment (≥ grade II Clavien-Dindo scale) will also be collected.

	VISITAS								
	Preselección	Selección	1-post	2-post	3-post	4-post	Alta	Final (28± 2 días)	Retirada prematura
Criterios de selección	х	х							
Entrega de	×								
documentación	X								
Firma Cl		х							
Variables		Y							
demográficas		X							
Comorbilidad		х							
ASA		х							
Medicación		Y							
preoperatoria		X							
CAM		х	х	х	х	х	х		x
BARTHEL		х							
MINIMETNTAL		х							
ECG con QTc		х			х				
RASS			х	х	х	х	х		x
Constantes vitales		х	х	х	х	х	х		х
Síntomas			v	v	v	v	v		v
extrapiramidales			X	X	X	X	X		X
Variables									
intraoperatorias			X						
EVA y analgesia			х	х	х	х			
Complicaciones no									
relacionadas con							х	x	x
delirio									
Mortalidad							х	х	
SF-36								х	
Datos analíticos		х	x*	x*	x*	x*	х		
Severidad del delirio			х	х	х	х	х		х
Tratamiento del delirio			x	x	x	x	x		x
Duración del delirio							х		х

Figure 1: Outline procedures in each visit. * At least one complete analysis during the period of admission.

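### Extrapyramidal symptoms are scored as present or absent after surgery with no check before the first dose, so signs the patient already had dilute the planned relative risk in both arms

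*Combined protocol and SAP*

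**What the plan says.** Section 1.14 (B.5) lists three safety variables: sedation on RASS, QTc prolongation, and "presence or absence of extrapyramidal symptoms (tremor, involuntary movements, stiffness". Section 5.1 repeats the third as "presence or absence of extrapyramidal symptoms (tremor, involuntary movements, rigidity". Neither section says that a sign must be new.

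The schedule in section 7.2 places the extrapyramidal check after surgery: "A daily personal clinical visit will be made to all randomized patients during the first four days of the postoperative period". It is listed again at the discharge and premature withdrawal visits. The selection-visit list (7.2 II) includes CAM, ECG with QTc, vital signs, Barthel and MiniMental, but no extrapyramidal check. Figure 1 agrees: the row for these symptoms ("extrapiramidales") is marked at the four postoperative days, discharge and premature withdrawal, and not under either selection column. Treatment starts before the first of these checks, since section 7.1 says "The first dose of active drug/placebo will be administered 60 minutes after arrival at the resuscitation unit".

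Section 6.2 removes several relevant groups: Parkinson's disease, vascular or Lewy body dementia, "Disorder of movements hipokinéticos", and "Patients on antipsychotic or antidopaminergic treatment". Section 7.2 II also records preoperative comorbidity. Section 10 plans relative risks with 95% confidence intervals, percentages and counts for categorical variables, and two-sided tests at 5%.

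**The concern.** QTc, the neighbouring safety variable, is defined as a change ("QTc prolongation: increase in mseg on the control ECG") and has an ECG at selection to measure it against. CAM is also done at selection, to rule out existing delirium. The extrapyramidal variable has no reference point of this kind, and the protocol gives no reason for the difference.

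Patients are 65 or older, and the Delphi entry score gives points for age, physical dependence and alcoholism. Some may arrive with a tremor or stiffness unrelated to any excluded diagnosis or drug. On a literal reading they are recorded as present on postoperative day 1, whichever capsule they received. The multivariate models in section 10 cannot adjust for a sign that was never recorded before dosing.

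Safety is the first secondary objective, and section 3 favours quetiapine partly because it is expected to cause few extrapyramidal effects. A variable whose relative risk drifts towards 1 leans towards the answer that the rationale already expects.

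**Working it through.** **The plan's own figure.** The plan gives no number for extrapyramidal symptoms. Its sample size (section 6.3) supplies the patients per arm. Taking 25% v 13% delirium (the upper end of the stated 20-25%, less 12 points), two-sided 5%, 80% power:

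n = [1.96·√(2·0.19·0.81) + 0.842·√(0.25·0.75 + 0.13·0.87)]² / 0.12² = 167 per arm. Then 167/0.95 = 176 per arm, or 352 in total, against the stated 350. The figure reproduces. With 5% losses, 175 × 0.95 ≈ 166 per arm are evaluable.

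**Assumptions.** The documents give no prevalence of pre-existing signs, no placebo rate and no rate for this regimen. Let b be the share of patients with a pre-existing sign (equal in both arms in expectation) and q the new-onset rate. The first scenario takes q = 2% on placebo and 10% on quetiapine. The 10% is the lower edge of the product-information band for the most frequent reactions (section 5.4).

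**Formulas.**
- Observed rate in an arm = b + (1 − b)·q.
- Observed risk difference = (1 − b)·(q₁ − q₀), so it shrinks only by the factor 1 − b.
- Power = Φ[(d − 1.96·SE₀)/SE₁], where d is the observed risk difference, SE₀ is the pooled and SE₁ the unpooled standard error, with 166 per arm.

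**Worked case, b = 5%.** Placebo: 0.05 + 0.95 × 0.02 = 0.069. Quetiapine: 0.05 + 0.95 × 0.10 = 0.145. Relative risk = 0.145/0.069 = 2.1; difference = 7.6 points. SE₀ = 0.0339, SE₁ = 0.0337, so power = Φ[(0.076 − 0.0665)/0.0337] = Φ(0.28) = 61%.

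**Results, 2% v 10%.** The last column counts only new signs in patients free of them at selection, with 166·(1 − b) per arm; there the relative risk stays at 5.0.

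| Pre-existing signs | Relative risk | Risk difference (points) | Power as planned | Power, new signs only |
|---|---|---|---|---|
| 0% | 5.0 | 8.0 | 87% | 87% |
| 1% | 3.7 | 7.9 | 81% | 87% |
| 2% | 3.0 | 7.8 | 76% | 86% |
| 5% | 2.1 | 7.6 | 61% | 85% |
| 10% | 1.6 | 7.2 | 44% | 83% |

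**A smaller drug effect, 2% v 5%.** With no pre-existing signs, relative risk is 2.5 and power about 32%. At b = 5%, relative risk is 0.0975/0.069 = 1.4 and power 15%. Counting only new signs brings power back to about 30%.

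**The case against.** A reader might infer that a long-standing tremor is being counted as a drug effect, or that quetiapine's own effect is hidden. The documents do not support that. In a randomised, double-blind, placebo-controlled comparison the drug effect is the difference between arms. Pre-existing signs fall equally on both in expectation and create no false harm. The risk difference hardly changes, and because section 10 also reports counts and percentages by arm, the absolute excess stays visible. The accurate word is diluted.

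A reader might also infer that only Parkinson's disease and hypokinetic disorders are screened out. Section 6.2 goes further: it also excludes antipsychotic or antidopaminergic treatment and Lewy body or vascular dementia. The main parkinsonian and drug-induced causes are therefore removed, and the remaining share may be small. These exclusions still do not record whether a sign is present before dosing.

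Assessors may discount an obviously old tremor, since the label says extrapyramidal and comorbidity is taken at selection. That helps in part, but the protocol gives them no such rule and no baseline examination to rely on.

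The magnitude depends on chosen rates. The product-information band is not specific to 150 mg in total over three days, and with 2% v 5% the trial has little power for this variable however it is defined. That objection stands: the change removes the dilution but does not make the trial large enough to detect a small excess.

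**Conclusion.** The gap is real and minor. The variable is plain presence after treatment starts, with no check before the first dose and no limit to new signs, so pre-existing signs from causes that are not excluded enter both arms. The loss falls on the planned relative risk and on power. Under 2% v 10%, a 1% to 10% background takes the relative risk from 5.0 to between 3.7 and 1.6, and power from 87% to between 81% and 44%; the risk difference loses at most 0.8 points. All of these figures rest on assumed rates and on recording every such sign literally. The delirium endpoint and the sample size are not affected.

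**What to change.** Add a yes/no check of each sign (tremor, involuntary movements, stiffness) to the selection-visit list in section 7.2 II, and mark the Selección column of Figure 1. In sections 1.14 and 5.1, define the safety variable as a new sign: absent at selection and present at a visit after the first dose. A patient who already has a sign does not count as a new case of that sign. Restrict the definition to new signs, because worsening cannot be scored from a yes/no check without a severity grade. Report the risk difference beside the relative risk.

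The cost is a minute or two per patient at a visit that already takes place, using the check already scheduled on four postoperative days. Patients with a pre-existing sign no longer contribute cases of that sign. Treating any such patient as lost altogether, as the calculation does, costs 4 points of power at a 10% background (87% to 83%). The check has to be made before dosing, since a baseline not recorded then cannot be recovered reliably later.

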3 JUSTIFICATION

According to the DSM-IV, delirium is an acute alteration of consciousness accompanied by inattention, disorganization of thought and alterations of perception that fluctuate in a short period of time. Postoperative delirium is one of the most common complications of surgery, with an incidence ranging from 10-51% in elderly patients at risk and up to 80% in those requiring critical care (1). It develops characteristically between 0 and 96 hours after the intervention (2) and is associated with a worse prognosis in the short and long term, with an increase in mortality and hospital stay and, therefore, an increase in economic expenses (3,4). The antipsychotic of choice for treatment is haloperidol (5,6), although its efficacy is limited in part by its side effects (mainly extrapyramidalism and prolongation of

the QTc interval) and lack of response in some patients. To solve these problems, second-generation or atypical antipsychotics appear, which have a more favorable safety profile with similar efficacy in clinical response (7). However, despite treatment, the prognosis does not seem to improve once delirium is triggered (4,8), so prophylaxis may be essential. Thus, although non-pharmacological prophylaxis measures (respect for wake-sleep cycle, pain control, early mobilization, providing visual and auditory aids...) have shown efficacy in reducing the incidence of delirium in this type of patients (4), this decrease is closely related to the complete follow-up of all measures, which implies a very important work overload without evidence of improvement in fundamental variables at discharge, such as functional or cognitive status (9). Therefore, pharmacological prophylaxis is gaining interest (4), although the evidence in the literature is limited. It seems logical to think that, just as antipsychotics are effective for the treatment of delirium, they will also be effective for pharmacological prophylaxis.

In this regard, a number of studies with haloperidol and atypical antipsychotics have presented variable results, possibly related to the quality of the studies, variability in the tools used for the diagnosis of delirium and the selection of high-risk patients. The first large randomized clinical trial was conducted in 430 postoperative hip replacement patients. It failed to demonstrate a reduction in the incidence of delirium when 1.5 mg haloperidol was administered orally divided into three doses, but the severity and duration of delirium decreased (10). Larsen (11), in 2010, tested olanzapine 5 mg orally in 400 patients and managed to demonstrate that the risk of developing delirium in the intervention group was lower (RR 0.36, 95% CI 0.24 to 0.52), although episodes of delirium were longer lasting and severe. In 2014, Fukata (12) administered 121 patients 2.5 mg of intravenous haloperidol daily after general, trauma or other surgery, and could not demonstrate a decrease in the incidence of delirium in the intervention group. And yet, Wang (1), using haloperidol in patients undergoing noncardiac surgery, demonstrated clinically significant incidence decreases. Despite the risk of bias in these studies, there was no evidence of adverse effects with the use of these antipsychotics at low doses.

We think that, within the group of atypical antipsychotics, quetiapine, due to its pharmacological profile (low affinity for dopamine receptors and μ receptors; high affinity for serotonergic receptors), could be useful in the prophylaxis of delirium and provide sedation without causing too many extrapyramidal effects (3) or precipitating acute episodes of delirium. In the current literature, there are no clinical trials with quetiapine for postoperative delirium prophylaxis but there are for the treatment of delirium. A series of randomized trials (7, 13,14) and one open-label trial (3) suggest that quetiapine may be effective and safe. Studies show faster resolution of symptoms than with placebo and find the same efficacy of other antipsychotics such as haloperidol, with low incidence of side effects, mainly drowsiness, without finding significant differences. The average dose used in these studies ranges from 40 mg to 200 mg, because they use increasing doses until symptoms are controlled. But there are studies that show efficacy with lower doses: 25-40 mg / day. They are studies carried out in the medical population and in critical care, and have certain limitations: n small, assessment of the effectiveness of treatment with quetiapine with different scales ... Even so, they would justify the use of quetiapine as prophylaxis at doses lower than those used for treatment. In this sense, there are two international clinical trials underway on postoperative delirium prophylaxis in the population at risk in critical care units, with an initial dose of quetiapine 12.5mg, in one of them adjusting for patient weight and the other with increasing doses as needed (15,16). Taking into account, in addition, that the clearance of the drug in patients over 65 years of age is decreased and, therefore, the half-life of the drug is extended in this population, we believe that the use of doses of quetiapine of 25 mg every 12 hours during the first three days of the postoperative period in patients at risk is justified.

One aspect to take into account is to determine the population at risk (in which we would suppose greater benefit of prophylactic measures), which can be complicated since until now there is no reliable

tool to detect patients at risk of developing delirium during the postoperative period (17). More and more risk factors for this condition are known that seem to be based on three variables (18): the first is the speed of onset of surgical aggression. Thishas been demonstrated in orthopedic surgery, where several studies show that urgent surgery is associated with increased risk of delirium. The second variable is severity: the greater the surgical aggression (for example aorta surgery or neurosurgery) and the longer the intervention, the greater the risk of delirium. Although there is little evidence linking increased risk of delirium with a drug or anesthetic technique, it currently appears that anesthetic depth plays an important role in the development of postoperative delirium with sufficient evidence (17,19). The last variable is the patient, in whom several risk factors have been identified: age (the older the older the greater the risk of delirium), cognitive deficit or dementia, depression, use of psychotropic drugs, associated comorbidity, degree of functionality (independent for activities of daily living)... (17-20).

In the work on the prophylaxis of delirium with antipsychotics, different tests have been used to identify patients at risk of developing delirium after surgery. One of the first was used by Kalisvaar to identify patients at risk of developing delirium after hip replacement surgery (21). Based on a scale of a study on delirium prophylaxis in patients undergoing general surgery, it used 4 items: visual deficit (measured with the Snellen test), APACHE II >16, Minimental Test > 24 and dehydration (BUN/creatinine ratio > 18). In this way, it classified patients with intermediate risk (if they had 1 or 2 items) or high risk if they had 3 or 4 (AUC 0.73). In 2014, Harasawa (22) used a new scale to predict the development of postoperative delirium in patients undergoing cerebrovascular surgery with a sensitivity of 71% and a specificity of 85.7%, area under the curve 0.844. It considers five variables: underlying disease (comorbidity), dehydration (nitrogen/creatinine index> 18), age >70 years, alterations in consciousness (Glasgow scale) and presence of depression-anxiety. Patients with a score greater than 12 were at increased risk of delirium. In that same year, in the published protocol of the HARPOON study (9), a multicenter trial that assesses the efficacy and safety of haloperidol prophylaxis in the prevention of delirium in elderly medical and surgical patients, they used three simple questions to identify patients at risk of developing delirium: about the patient's mental state (do they have memory problems?), on the degree of functionality (have you required help for your personal care in the last 24 hours?) and on the background (have you presented a state of transitory confusion during admissions or previous illnesses?). Each positive response scores as 1, and a score equal to or greater than 1 identifies a patient at risk. Except in this last study, the use of delirium risk predictor scales is complicated by the incorporation of other scales that hinder and slow down their realization. In this sense, in 2016 a delirium prediction scale was published to identify high-risk patients based on clinical data from the perioperative period: it is the Delphi method (23). The predictors used are: age, dependence for physical activities, alcoholism, hearing deficit, history of delirium, urgent surgery, open surgery, C-reactive protein value > 10 (mg/mL) and admission to critical care unit. A score equal to or greater than 7 classifies the patient as at high risk of developing delirium during the postoperative period. This predictor scale presents an area under the curve of 0.938 (95% CI: 0.91-0.97) and identifies the patient at high risk of developing delirium with a sensitivity of 80.8% and a specificity of 95.7%. It is simple, fast and easy to perform.

Given the importance of this condition, its prevalence and its consequences, we think that prophylaxis in the population at risk (patients >65 years postoperative for non-cardiac surgery) during the first 72 hours after surgery with small doses of quetiapine can provide great benefits (decreased incidence, decreased duration and severity delirium) with a low level of risk since it has a favorable safety profile.

